10.2.3 Post-baseline assessment

Post-baseline assessment is any assessment performed after baseline and up to EOS.

10.2.4 Treatment start date/time

Treatment start date/time is the date/time recorded in the 'Study Treatment Administration' CRF page.

10.2.5 Definition of end of study treatment

Not applicable.

10.2.6 Definition of End-of-Study

EOS for a single subject is defined as the day when safety follow-up assessments are performed.

For randomized subjects who never received the study treatment, EOS date is defined as the earliest date amongst the following, as reported in the “Study Discontinuation” CRF page:

1. Date of last successful contact,
2. Date of subject decision,
3. Date of physician decision,
4. Date of subject death,
5. Date subject was informed of sponsor’s decision.

10.2.7 Definition of screening failure

A subject is considered a screening failure if he/she was not randomized (i.e., has not been assigned a study drug).

10.2.8 Definition of premature study discontinuation

Subjects are considered to have prematurely discontinued the study if a reason for stopping the study is provided on the Study Discontinuation CRF page.

The date and the reason for study discontinuation are collected in the “Study Discontinuation” form (and in the “Death” form if the subject died).

10.3 Definition of reason for screening failure

For subjects who are considered a screening failure, the reason for screening failure is as reported in the CRF.

10.4 Convention for demography data considered for analysis when multiple values reported

For subjects with multiple baseline assessments, only the last values are included in any analysis, while all values will be presented in the listings and date of informed consent signature will remain the date of the first signature.

10.5 Coding dictionaries

The version of MedDRA used for coding medical history and AEs will be displayed in statistical output footnotes.

Similarly, the version of the WHO Drug Reference Listing dictionary based on the WHO ATC classification system used for coding of previous and concomitant therapies reported in this study will be displayed in statistical output footnotes.

10.6 Medical history and current (study concomitant) medical conditions

Medical history and current medical conditions, i.e., study concomitant medical conditions, at baseline include previous and/or concomitant procedures or diagnoses.

Medical procedures will be identified as medical history, i.e., ended prior to informed consent signature date, and as concomitant, for those ongoing at or after the signature date of the informed consent.

If none apply, procedures and diagnoses are considered *study concomitant medical conditions*.

10.7 Previous and concomitant medication

Previous medications are defined as any medication with a start date prior to study start date [see definition in Section 10.2.1] and with an end date (last administration) prior to study start date.

Study concomitant medications are defined as any medication that is ongoing on the date when informed consent is obtained, or initiated at any time between study start and up to EOS [see definition in Section 10.2.6].

Study-treatment concomitant medications at baseline (a subset of study-concomitant medications) are defined as any medication with “started prior to first study treatment administration” indicated as “yes” or with a start date before date of study treatment administration and is either ongoing at end of study or has an end date after the study treatment administration date.

Study-treatment concomitant medications (a subset of study-concomitant medications) are any *study-treatment concomitant medications at baseline* and any medications initiated within the 48-hour (2-day) period from study treatment administration.

If no end date is available for a medication, it is considered ongoing at EOS.

11 CHANGES OR CLARIFICATIONS TO ANALYSES PLANNED IN THE STUDY PROTOCOL

11.1 Changes to the analyses planned in the study protocol

11.1.1 Change in sensitivity analysis

The protocol indicated that the sensitivity analysis for the PD endpoints was to be conducted on the FAS. This will not be performed, as the main difference between the FAS and mFAS is the presence of a PRU measurement 30 minutes after study drug administration, a condition required to perform the analysis on the FAS as no imputation is planned for this endpoint.

11.1.2 Study drug exposure

The protocol specified that study drug exposure was to be analyzed on the FAS and the PPS (sensitivity analysis). This has been modified so that the analysis of study drug exposure is performed on the SAF, the definition of which is the same as the FAS but provides better consistency for safety data interpretation.

11.2 Changes in the conduct of the study / data collection

Not applicable.

11.3 Clarifications concerning endpoint definitions and related variables or statistical methods

Analysis set

The PPS definition has been modified to use the analysis set used for analysis of primary endpoint as a reference. Instead of using the FAS as the reference set to define the PPS, the mFAS is used and is more relevant as this analysis set is the one used for performing the analyses on the primary PD endpoint.

The protocol indicated that analysis of *demographics characteristics* would be performed on the RND only if there was a difference between the RND and the set used for the main analysis (FAS). The SAP now requires that this analysis is performed on the RND as well, regardless of the difference to the FAS, unless the RND includes exactly the same subjects, in which case the analysis on the RND is not needed.

11.4 Additional analyses as compared to the study protocol

Not applicable.

12 LIST OF TABLES, LISTINGS AND FIGURES

A complete list of tables, listings and figures is provided in the *SAP Appendix - List of statistical outputs* document.

13 APPENDICES

Appendix A Protocol synopsis

PROTOCOL SYNOPSIS ID-076A202

TITLE	A multi-center, open-label, randomized study to assess the onset of platelet aggregation inhibition after a single subcutaneous injection of ACT-246475 in adults with acute myocardial infarction.
OBJECTIVES	
Primary objective
 
The primary objective of the study is to assess the inhibition of platelet aggregation (IPA) 30 minutes after a single subcutaneous (s.c.) injection of ACT-246475 in subjects with acute myocardial infarction (AMI) receiving conventional antithrombotic treatment (e.g., aspirin, oral P2Y₁₂ receptor antagonists, anticoagulants).
 
Other objectives
 
The other objectives of this study are:
 
• To assess the pharmacokinetics (PK) of ACT-246475 in subjects with AMI.• To investigate safety and tolerability of ACT-246475.
DESIGN	
This is a prospective, multi-center, open-label, randomized, parallel-group, Phase 2, exploratory study of a single s.c. administration of ACT-246475, at two different dose levels, in subjects with AMI (ST-segment elevation MI [STEMI] or non-STEMI [NSTEMI]) scheduled for invasive strategy.
 
Approximately 42 adult subjects with confirmed diagnosis of AMI (STEMI or NSTEMI), and time from onset of symptoms of more than 30 min and less than 6 hours, will be randomized to receive ACT-246475 at the dose of either 8 mg or 16 mg, in a 1:1 ratio, injected s.c. in the thigh in addition to conventional standard-of-care treatment. Injection of ACT-246475 will be performed as soon as possible after randomization.
 
The study comprises the following consecutive periods:
 
Screening period: Starts when the subject gives informed consent (orally or in writing as described in Section 1.4.3) and ends with subject's randomization.

	Treatment period: Starts with subject's randomization and ends after the End-of-Study (EOS) assessments, approximately 48 h after the administration of a single study treatment dose.
PLANNED DURATION	Approximately 4 months from first subject, first visit to last subject, last visit.
SITES / COUNTRIES	Approximately 3–8 sites in 1–2 countries are planned.
INCLUSION CRITERIA	
 1) Informed consent obtained prior to any study-mandated procedure. 2) Males aged from 18 to 85 and postmenopausal females aged up to 85 years. Postmenopausal is defined as 12 consecutive months with no menses without an alternative medical cause. 3) Onset of symptoms of AMI of more than 30 min and less than 6 hours prior to randomization. 4) Subjects presenting a type I AMI including STEMI or NSTEMI defined as follow: 
 a) STEMI: new persistent ST-segment elevation ≥ 1 mm (1 mV) in two or more contiguous ECG leads, or b) NSTEMI: ECG changes compatible with myocardial ischemia without persistent ST-segment elevation and elevated troponin defined as a troponin T or I level $\geq 1.5 \times$ the upper limit of normal. 5) Estimated body weight ≥ 40 kg (88 lbs).
EXCLUSION CRITERIA	
Conditions associated with the qualifying AMI:
 
 1) Cardiogenic shock or severe hemodynamic instability (e.g., Killip class 3–4). 2) Cardiopulmonary resuscitation. 3) Loading dose of any oral P2Y₁₂ receptor antagonist prior to randomization. 
Bleeding risks:
 
 4) Active internal bleeding, or bleeding diathesis or conditions associated with high risk of bleeding (e.g., clotting disturbances, gastrointestinal bleed, hemoptysis). 5) Known clinically important anemia. 6) Oral anticoagulation therapy within 7 days prior to randomization.

	
7) Planned fibrinolytic therapy or any fibrinolytic therapy administered within 24 h prior to randomization.
 
8) Known platelet disorders (e.g., thromboasthenia, thrombocytopenia, von Willebrand disease).
 
Conditions that may either put the subject at risk or influence the results of the study:
 
9) End-stage renal failure requiring dialysis.
 
10) Any clinically significant findings on a physical exam, or laboratory tests that in the investigator's judgment would preclude safe or reliable participation of a subject in the study.
 
11) Concomitant diseases (e.g., advanced liver cirrhosis, mental illness, neurodegenerative disease, terminal malignancy...) or conditions (e.g., inability to communicate well with the investigator in the local language) that, in the opinion of the investigator, may put the subject at risk, prevent the subject from complying with study requirements or may be a confounder for the study interpretation.
 
12) Clinically relevant skin disease that prevents s.c. injection in the thigh, according to the investigator's judgment.
 
13) Known use of inhibitors of OATP1B1 or OATP1B3 (e.g., ritonavir, clarithromycin, erythromycin, cyclosporine, gemfibrozil) at screening.
 
14) Known hypersensitivity to ACT-246475, any of its excipients, or drugs of the P2Y₁₂ class.
 
15) Previous exposure to an investigational drug within 3 months prior to screening.

STUDY TREATMENTS	
Investigational treatment
 
Study treatment for s.c. administration will be available as sealed glass vials in 1 strength: 20 mg. The vials contain 22 mg of lyophilized ACT-246475A (hydrochloride salt of ACT-246475) to be reconstituted with 1 mL of water for injection. Further dilution with 1 mL NaCl 0.9% will be performed for preparation of the dose of 8 mg. The s.c. formulation contains mannitol as an inactive ingredient.
 
Study treatment will be given as a single dose of ACT-246475 (8 or 16 mg) in a volume of 0.8 mL, administered s.c. in the thigh at site by qualified personnel (e.g., nurse, physician).

CONCOMITANT THERAPY	
Allowed concomitant therapy
 
Standard treatment of AMI is allowed including anticoagulants and oral P2Y₁₂ receptor antagonists.
 
When initiation of an oral P2Y₁₂ receptor antagonist is considered for a subject, it must be initiated after administration of ACT-246475. In absence of clinical data regarding administration of an irreversible P2Y₁₂ antagonist following the administration of ACT-246475, it is requested to use a reversible oral P2Y₁₂ receptor antagonist (e.g., ticagrelor).
 
Forbidden concomitant therapy
 
The following medications are prohibited from screening and up to the last PK blood collection:
 
• Fibrinolytic therapy (e.g., streptokinase, alteplase...).• OATP1B1 and OATP1B3 inhibitors (e.g., atazanavir, ritonavir, lopinavir, simeprevir, clarithromycin, erythromycin, cyclosporine, eltrombopag, lapatinib, gemfibrozil, rifampin).• Glycoprotein IIb/IIIa inhibitors.• Oral irreversible P2Y₁₂ antagonists (clopidogrel or prasugrel).• Cangrelor.
ENDPOINTS	
Primary endpoint
 
The primary endpoint is the response to the treatment defined for each subject as a P2Y₁₂ reaction units value < 100 at the 30 min post-dose time point, as measured via VerifyNow[®]. This corresponds to an IPA induced by ADP > 80%.
 
Safety endpoints
 
The safety endpoints will be assessed up to EOS, i.e., over 48 hours post treatment administration:
 
• Treatment-emergent adverse events (AEs)¹ and serious adverse events.• AE of specific interest (AESI): Hemorrhage.

¹ A treatment-emergent AE is any AE temporally associated with the administration of study treatment (until 48 hours after study treatment administration) whether or not considered by the investigator as related to study treatment.

	
• Change in vital signs (systolic and diastolic arterial blood pressure and pulse rate) from baseline to all assessed time points during the study.• Change from baseline for clinical laboratory tests.• Treatment-emergent marked laboratory abnormalities. 
Pharmacokinetic endpoints
 
PK endpoints include maximum plasma concentration (C_{max}) and time to reach C_{max} (t_{max}).

ASSESSMENTS	Refer to the schedule of assessments in Table 2.
STATISTICAL METHODOLOGY	
Analysis sets
 
The Screened analysis set includes all subjects who are screened and have a subject identification number.
 
The Randomized analysis set includes all subjects who have been assigned to a study treatment.
 
The Full analysis set (FAS) includes all randomized subjects who have been administered the study treatment.
 
The modified FAS (mFAS) includes all subjects from the FAS who have an assessment of the primary endpoint.
 
The Per-protocol set includes all subjects from FAS who complied with protocol sufficiently to allow adequate estimation of the treatment effects (criteria for sufficient compliance will be detailed in the statistical analysis plan).
 
The Safety analysis set (SAF) includes all subjects who received at least one dose of study treatment.
 
The PK analysis set includes all subjects in the SAF who have at least one PK sample collected after administration of study treatment.
 
Main analysis
 
The primary analysis will be conducted using the mFAS and will consider the treatment actually received (which may differ from the assigned one).
 
The analysis of the primary endpoint will be performed for each of the two treatment doses independently, i.e.,

considering 2 null hypotheses (proportion of patients achieving a response is less or equal to 50%) at 0.025 type I error each.

The study will be declared positive with regard to the primary objective, if at least 1 of the 2 null hypotheses is rejected at 0.025 type I error level.

Subjects without primary endpoint assessment will be replaced.

A one-sided z-test will be computed and the 95% confidence interval of the proportion of responders will be provided.

Summary of response, in terms of number (%) of responding subjects, will be provided.

Sample size

The sample size is based on the study primary objective of assessing IPA 30 min after ACT-246475 administration, as assessed by the proportion of subjects achieving a response (i.e., P2Y₁₂ reaction units [PRU] < 100 at 30 min post study drug administration). The sample size should be sufficient to allow the rejection at least one of the null hypotheses.

The study should include 21 subjects evaluable for the primary pharmacodynamic endpoint in each arm considering:

- an overall two-sided type I error of 0.05, adjusted for multiplicity using the Bonferroni method for each of the 2 null hypotheses (testing each dose at an alpha level of 0.025),
- a power of 90%, and
- the following assumptions for the response rate under the null and alternative hypotheses as reported in the table below.

Proportion of responders under H ₀	Proportion of responders under H ₁	Number of subjects (total)	Number of subjects (per arm)
50%	85%	42	21

STUDY COMMITTEES	
The Independent Safety Event Committee (ISEC) involved in the ID-076A201 study will also review safety data from this study. It consists of two independent clinical experts who will review safety data independently from the sponsor during the study. The ISEC has overall responsibility for safeguarding the interests of subjects by monitoring safety data obtained in the study and making appropriate recommendations based on the reported data. The ISEC will be fully operational prior to enrollment of the first subject into the study.
 
The ISEC will specifically focus on study-drug-related clinically relevant major bleeding events, according to the thrombolysis in myocardial infarction (TIMI) definition.

------------------	---

Appendix B Protocol deviation list

The actual list of protocol deviations leading to exclusion from analysis set will be updated prior to study closure if required.

The table below provides the reasons considered for excluding subjects from analysis set.

Table 4 Definition of exclusions from analysis sets

Reason for exclusion from set	Reason	Programmable condition
Screened set	Informed consent not initially obtained for the study	no record in DS where DS.DSDECOD='INFORMED CONSENT OBTAINED' or DS.DSSTDTC='' when DS.DSDECOD='INFORMED CONSENT OBTAINED'
Randomized set	Not randomized	no DS.RANDNO
Full Analysis set	Subject did not get study treatment	EX.EXDOSE not >0
Modified FAS	30-minute post-dose VerifyNow [®] blood sample missing	missing LB.LBSTRESN where LB.LBTESTCD= P2Y12RU and LB.LBTPT= 30 MINUTE POST DOSE
Safety Set	Subject did not get study treatment	EX.EXDOSE not >0
Per Protocol set	Subject included without a type 1 MI	MH.MHLLT='Acute myocardial infarction type 2' (LLTCD=10079263) where MH.MHENRTPT='ONGOING' and MH.MHENTPT='INFORMED CONSENT' or at least one record with IE.IETESTCD = INCL04
Per Protocol set	Onset of AMI symptoms more than 6 hours prior to randomization	at least one record with IE.IETESTCD = INCL03
Per Protocol set	Subject included with severe hemodynamic instability	at least one record with IE.IETESTCD = EXCL01
Per Protocol set	Subject received a loading dose of oral P2Y ₁₂ receptor antagonist prior to randomization	at least one record with IE.IETESTCD = EXCL03
Per Protocol set	Subject with concomitant important anemia	at least one record with IE.IETESTCD = EXCL05

Per Protocol set	Subject with concomitant platelet disorders	at least one record with IE.IETESTCD = EXCL08
Per Protocol set	Subject with concomitant disease or condition that may have prevented subject from complaining with study requirements of may be a confounder of study interpretation.	at least one record with IE.IETESTCD in(EXCL12, EXCL14, EXCL15)
Per Protocol set	Incorrect administration of the study drug	DV.DVREFID = 02C01, 02C02
Per Protocol set	30-minute post-dose VerifyNow® blood sample collected outside of the protocol-defined window	DV.DVREFID = 03F03 or computed as need be
Per Protocol set	Issues with blood sample collection or processing for platelet aggregation assays	DV.DVREFID = 03F10, 03F08
Per Protocol set	Treatment with forbidden i.v. platelet inhibitors before assessment of the 30-minute time point.	DV.DVREFID = 04A02
PK set	Subject does not have at least one plasma concentration measurement after administration of study treatment	all PC.PCSTRESC = « » when PC.PCTPT not PRE-DOSE

AMI, acute myocardial infarction; i.v., intravenous; PK, pharmacokinetic set.

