**Conditions that may either put the subject at risk or influence the results of the study:**

- 9) End-stage renal failure requiring dialysis.
- 10) Any clinically significant findings on a physical exam, or laboratory tests that in the investigator's judgment would preclude safe or reliable participation of a subject in the study.
- 11) Concomitant diseases (e.g., advanced liver cirrhosis, mental illness, neurodegenerative disease, terminal malignancy...) or conditions (e.g., inability to communicate well with the investigator in the local language) that, in the opinion of the investigator, may put the subject at risk, prevent the subject from complying with study requirements or may be a confounder for the study interpretation.
- 12) Clinically relevant skin disease that prevents s.c. injection in the thigh, according to the investigator's judgment.
- 13) Known use of inhibitors of OATP1B1 or OATP1B3 (e.g., ritonavir, clarithromycin, erythromycin, cyclosporine, gemfibrozil) at screening.
- 14) Known hypersensitivity to ACT-246475, any of its excipients, or drugs of the P2Y12 class.
- 15) Previous exposure to an investigational drug within 3 months prior to screening.

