#### **10.3.1 Overall testing strategy**

The study is intended to assess the IPA 30 min after a single s.c. injection of ACT-246475.

It will be declared to be positive with regard to the primary objective if for at least one of the two tested doses of ACT-246475, the corresponding null hypotheses is rejected at the 0.025 alpha level.

No imputation will be considered for handling missing values in the main analysis of PD.

Imputations may be performed in sensitivity/exploratory analyses, if deemed necessary, e.g., more than 10% missing values at a given time point.

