#### ***10.3.3.2 Handling of missing data***

Subjects for whom the determination of the response is not possible, i.e., who have not received ACT-246475 or with a missing 30 min post-study drug administration assessment, will be replaced; no imputation will be considered.

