6.8.3 Handling of missing data

No imputations are planned.

Subjects for whom determination of the PD response is not possible will not be included in the computation of response rate for the main analysis.

The same approach will be considered for the exploratory endpoint PD response within the 1st hour.

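### SAP Table 4 programs the per-protocol exclusion worded as criterion 11 to criteria 12, 14 and 15, and the 30-minute response lacks a planned check for missing samples and has only a conditional one for mistimed samples

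*SAP*

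**What the plan says.** **PPS exclusion row.** One row of SAP Appendix B, Table 4, gives as its reason "Subject with concomitant disease or condition that may have prevented subject from complaining with study requirements of may be a confounder of study interpretation". Its programmed condition is "at least one record with IE.IETESTCD in(EXCL12, EXCL14, EXCL15". Protocol 4.4, criterion 11, covers concomitant diseases or conditions that may "prevent the subject from complying with study requirements or may be a confounder for the study interpretation". Criterion 12 is "Clinically relevant skin disease that prevents s.c. injection in the thigh", criterion 14 is hypersensitivity and criterion 15 is recent exposure to an investigational drug. On later changes, the appendix says: "The actual list of protocol deviations leading to exclusion from analysis set will be updated prior to study closure if required".

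**Missing 30-minute PRU.** Under protocol 10.3.3.2, subjects "with a missing 30 min post-study drug administration assessment, will be replaced; no imputation will be considered". SAP 6.8.3 states: "Subjects for whom determination of the PD response is not possible will not be included in the computation of response rate for the main analysis". It plans no imputation. SAP 11.1.1 drops the protocol's FAS sensitivity analysis because, without imputation, it needs the same 30-minute value. Protocol 10.3.1 had left room for more: "Imputations may be performed in sensitivity/exploratory analyses, if deemed necessary", with more than 10% missing at a time point as its example.

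**Mistimed samples.** Protocol Table 2 sets the window at 30 ± 5 minutes, but SAP 6.8.1.1 assigns PRU by planned time. Out-of-window and mishandled 30-minute samples are excluded only from the PPS (SAP Table 4). SAP 6.8.1.3 repeats the main analysis on the PPS only if it is at least 10% smaller than the mFAS. SAP Table 2 and protocol Table 3 say more than 10%.

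**The concern.** The Table 4 row is a programming specification, and SAP 4.1.5 points to Appendix B for the detailed PPS criteria. If it is run as written, a subject who violated criterion 11 stays in the PPS. Violators of criteria 12, 14 or 15 leave it under a reason that does not describe them.

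The other two points concern how far each dose's 30-minute result can be tested for robustness. Each dose is tested separately on about 21 subjects, so a few subjects can matter. Subjects who were dosed but gave no 30-minute value disappear from the 30-minute response rate. Samples taken at the wrong time count as 30-minute samples in a study of onset of action. The one analysis that would remove them depends on a threshold applied to the two arms together.

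**Working it through.** **Code check.** Table 4's eligibility codes against protocol 4.3 and 4.4:

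| Code in Table 4 | Reason in Table 4 | Protocol criterion of that number | Match |
|---|---|---|---|
| INCL03 | Symptom onset beyond 6 h | Onset between 30 min and 6 h | Yes |
| INCL04 | Not a type 1 MI | Type I AMI | Yes |
| EXCL01 | Severe hemodynamic instability | Shock or severe instability | Yes |
| EXCL03 | Oral P2Y12 loading dose before randomization | Same | Yes |
| EXCL05 | Important anemia | Same | Yes |
| EXCL08 | Platelet disorders | Same | Yes |
| EXCL12, 14, 15 | Concomitant disease or condition, compliance or confounding | Skin disease; hypersensitivity; investigational drug | No |

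Six of six other codes follow the protocol's numbering, so a different numbering scheme does not explain the seventh row.

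**Inputs for the arithmetic.** 21 evaluable per arm, 42 in total, null 50%, target 85%, power 90% (protocol 10.5); alpha 0.025 per dose. SAP 6.8.1.2 describes the test as two-sided in one place and one-sided in another. Both critical values are therefore used: 2.241 (two-sided) and 1.960 (one-sided).

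**The plan's own figure.** n = [(z_alpha·√(p0·q0) + z_beta·√(p1·q1)) / (p1 − p0)]²
- Two-sided 0.025: [(2.241 × 0.5 + 1.282 × 0.357) / 0.35]² = 20.3, so 21 (power at 21 is 91.2%). This reproduces the plan.
- One-sided 0.025: 16.9, so 17. This does not.

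**Missing counted as non-response.** z = (x/n − 0.5) / √(0.25/n). The documents give no missing rate, so 1 to 6 missing subjects per dose are considered.

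| Observed | z | Missing needed to reverse, two-sided | Missing needed to reverse, one-sided |
|---|---|---|---|
| 15/21 | 1.964 | already fails | 1 (15/22, z = 1.706) |
| 16/21 | 2.400 | 1 (16/22, z = 2.132) | 2 (16/23, z = 1.877) |
| 17/21 | 2.837 | 3 (17/24, z = 2.041) | 4 (17/25, z = 1.800) |
| 18/21 | 3.273 | 4 (18/25, z = 2.200) | 6 (18/27, z = 1.732) |

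At a true rate of 85%, Binomial(21, 0.85) gives P(X = 16) = 11.5% and P(X = 15) = 5.4%. These are the chances of landing exactly on the two-sided and one-sided boundary.

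**PPS trigger.** 4/42 = 9.5% (not run); 5/42 = 11.9% (run). Four exclusions in one arm are 4/21 = 19.0% of that dose group. The trigger is 5 under both wordings for an mFAS of 41 to 49. At 40 it is 4 (at least 10%) or 5 (more than 10%); at 50 it is 5 or 6.

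**Effect of removing mistimed responders.**
- One removed from 16/21: 15/20, z = 2.236, which just fails two-sided.
- Four removed from 17/21: 13/17, z = 2.183, which fails two-sided and passes one-sided.
- Four removed from 18/21: 14/17, z = 2.668, which passes both.

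**The case against.** **On the code.** Table 4 is selective: EXCL02, 04, 06, 07, 09, 10 and 13 are also in no row. Labels are loose elsewhere too; the INCL03 row omits the 30-minute lower limit. The label rather than the code could be wrong. The PPS is a conditional supportive set, eligibility waivers are not permitted, and the list can still be updated. This stands in part. The documents do not prove which side is in error, and few subjects may be affected. But label and code conflict, and permission to update the list does not correct it.

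**On missing values.** The protocol pre-specified replacement without imputation, and its provision for sensitivity imputation was optional. Dropping an FAS analysis without imputation loses nothing, because it equals the mFAS analysis. SAP 5.3.1 tabulates set sizes by dose and the main analysis gives responder counts, so responders divided by FAS size can be worked out by hand. All of that is correct. The FAS analyses of first-hour response, 60-minute status and PRU over time can also use these subjects, but none of them estimates the 30-minute response rate. No planned table gives that rate, its interval or its test with these subjects counted.

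**On mistimed samples.** The 10% rule comes from the protocol, deviations and exclusion reasons are listed, and the trigger of 5 assumes an mFAS near 42. That the rule pools the arms is inferred from its reference to set size; no per-arm rule is given. These points limit the concern but do not remove it.

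**On size.** The single-subject reversals are boundary cases. At 85% in both arms, the chance that one dose has exactly 16 responders and the other 15 or fewer is 2 × 0.115 × 0.083 = 1.9% under the two-sided rule, before requiring any missing subject. If four exclusions fall at random and one arm has 17/21, the chance that all four are responders in that arm is C(17,4)/C(42,4) = 2.1%. This is a fair limit on the effect on the study's conclusion.

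**Conclusion.** The concern holds, with high confidence. The main point is the Table 4 row: as coded, it builds a PPS that does not match its written definition. This assumes that the code numbers follow the protocol's criteria, as they do in the six other rows.

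The robustness gaps are also real but modest. No planned 30-minute analysis counts dosed subjects without a 30-minute PRU. With the planned mFAS of 42, up to four PPS exclusions, even all in one arm, lead to no PPS analysis. A dose-level result at the boundary can turn on one subject, whereas 18/21 withstands three missing-as-failure subjects under the two-sided rule and five under the one-sided rule. The study conclusion would differ only if the other dose also failed. The mFAS result remains the declared result, so these changes should be made but do not alter the primary analysis.

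**What to change.** 1. Code the Table 4 row to EXCL11. Keep EXCL12, EXCL14 and EXCL15 only as separately worded rows, if excluding those subjects is intended. This also resolves the matter if the label was the error.
2. Add one supportive sensitivity table per dose on the FAS, counting a missing 30-minute PRU as non-response.
3. Present the PPS analysis by dose whenever the PPS differs from the mFAS, without the pooled 10% condition.

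The cost is one code correction and two or three extra tables. Sample size, conduct and the primary analysis stay as they are. The downside is that a supportive result may look less favourable than the mFAS result. Counting every missing value as non-response is deliberately conservative, since some will be assay failures, and the table should say so.
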